**Table 1: Schedule of Assessments**

Study Visit (Month)	Study Day (±Visit Window)	Treatment Period												AT F/U b,c
		Onset Period		Efficacy Period										
		Baseline		Month 1		Month 2	Month 3	Month 4	Month 5	Month 6	Month 7	EOT	EOS/ET a,b	
		Day 1	15 ±3	29 ±7	43 ±3	57 ±7	85 ±7	113 ±7	141 ±7	169 ±7	197 ±7	225 ±7	253 ±7	281 ±7
Serum Chemistry o	X	X	X	X	X	X	X	X	X	X	X	X	X	X
Liver Function Tests p	X	X	X	X	X	X	X	X	X	X	X	X	X	X
Anti-Drug Antibodies k,n,q	X	X		X			X					X	X m	
Hematology o	X	X	X	X	X	X	X	X	X	X	X	X	X	X
Hepatic Tests p	X													
Exploratory Biomarkers k		X					X						X	
Exploratory Circulating RNA (Optional) k		X					X						X	
Exploratory DNA Sample (Optional) k		X												
Plasma PK k,r		X		X			X				X	X		
Urinalysis	X	X											X	
Urine Collection for Biomarkers k		X					X						X	
HJHS s		X											X s	
Patient Resource Use s		X											X s	
EQ-5D s		X											X s	
Haem-A-QOL / Haemo-QOL s		X											X s	
HAL / pedHAL s		X											X s	

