**Note:**

- See Section 7 for study assessment instructions.
- Any Screening assessments performed within 7 days prior to baseline do not need to be repeated at the Baseline visit.
- Rescreening of patients is permitted with consultation of the study Medical Monitor.
- Laboratory parameters are described in Section 7.5.5 and listed in Table 5.
- As clinical research parameters, TG, D-dimer, and all other non-safety laboratory parameter results will not be communicated to sites. AT and factor results will be provided at screening for confirmation of eligibility. AT results will be provided at AT follow-up visits for monitoring.
- When scheduled at the same time points, vital signs and 12-lead ECGs will be performed before the physical examinations and blood/urine sample collections.
- Unless otherwise specified, assessments on dosing days are predose.

- a Not required at Early Termination Visit for patients who complete assessment at EOT Visit and subsequently Early Terminate.
- b Patients in the fitusiran treatment arm who discontinue IMP dosing for any reason and agree to complete the remaining assessments through the EOS/ET visit and AT follow-up and may receive treatment consistent with local standard practice for their disease per Investigator judgment, once AT levels return to ~60% (per the central laboratory) or per Investigator discretion in consultation with the study Medical Monitor. For patients who withdraw from the study early and do not consent to complete remaining assessments through the EOS/ET visit and AT follow-up visits, every effort should be made to conduct the assessments performed at the EOS/ET visit.
- c Patients in the fitusiran treatment arm not enrolling in the extension study will complete AT F/U visits at monthly intervals following final fitusiran dose until AT activity level returns to ~60% (per the central laboratory) or per Investigator discretion in consultation with the study Medical Monitor.
- d The complete medical history/disease history (ie, including bleeding episode and treatment history over the prior 6 months) to be recorded at Screening.
- e Randomization may occur within 3 days prior to Day 1.
- f eDiary training will be completed at the Clinic at Screening (see Section 7.2.1).
- g A full physical exam will be performed at Screening only; a directed physical exam will be performed at all other visits (see Section 7.5.3).

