- q All patients will be tested for antibodies to fitusiran at the Screening visit. After randomization, testing for antibodies to fitusiran will be performed in the fitusiran treatment arm only.
- r Blood samples for PK analysis will be collected at the time points listed in Table 7 in all fitusiran arm patients. In East Asian patients in the fitusiran arm at East Asian sites, blood samples for PK analysis will be collected at the time points listed in Table 8 (which includes all those time points listed in Table 7), and pooled urine samples will be collected for PK analysis at the time points listed in Table 9.
- s Must be completed at the clinic. Will be collected at EOS visit; not collected at ET visit.
- t Will include review of entries, (symptoms of bleed events, bleed causality, bleed severity, doses administered), whether appropriate site contact occurred regarding treatment of bleeds, and review of patient bleed management plan and recommendations and requirements for site contact regarding dosing.
- u It is strongly preferred that BPA administration and bleeding events are entered in the eDiary immediately or within 24 hours. Additional patient follow-up may be required as described in Section 7.2.1. Patients in the fitusiran treatment arm who present in the clinic with symptoms characteristic of a potential bleeding episode should have assessments completed per Table 2.
- v Perioperative assessment safety and hemostatic efficacy only in patients undergoing operative procedures while on study (see Table 10).
- w AEs will be monitored and recorded from date of signed informed consent through Follow-Up. Signs and symptoms of thrombosis will be evaluated at every visit (see Section 6.5)
- x In addition to recording concomitant medications, documented history of prior medications will be collected during Screening.

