### **7.6. Other Assessments**

#### **7.6.1. Patient-reported Outcomes**

Patient-reported outcomes will be utilized in this study where available to assess HRQOL, physical activity, and treatment satisfaction and health utility. The age of the patient at randomization will determine which age-specific questionnaires will be utilized, and will be in force for the study duration. All completed questionnaires or instrument forms for the patient-reported outcome assessments described below will be collected, entered into a database, and archived according to the Study Manual.

The Sponsor or designee will provide the translations for all survey instruments, where translations are available. The sites must not translate any survey instruments.

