5.2 General Methods

All data listings that contain an evaluation date will contain a study day relative to the day of Day 1 visit when baseline assessments are performed and fitusiran first dose is given, which is designated as Day 1. The Day 1 visit date should coincide with randomization date but could occur within 3 days after the randomization. If the fitusiran first dose is given after Day 1 visit, a study day will be calculated relative to the day of first dose. Study days will be calculated as evaluation date – Day 1 visit date (or first dose date) +1 and pre-Day 1 visit days will be calculated as evaluation date – Day 1 visit date (or first dose date). For example, the day prior to Day 1 visit will be Day –1 and the day after Day 1 visit will be Day 2, etc. There will be no Study Day 0.

Categorical variables will be summarized using counts and percentages. Continuous variables will be summarized using the number of patients (n), mean, SD, median, interquartile range (Q1, Q3), minimum value (min), and maximum value (max). The precision of the measurement for each continuous variable will be used to determine the number of decimal places to present in tables, figures and derived listings. Minimum and maximum values will be reported with the same precision as the units of measure. The other statistics will be reported to 1 greater decimal place. Any values that require transformation to standard units (metric or SI) will be converted with the appropriate corresponding precision.

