5.5 Baseline Definitions

Unless noted otherwise, baseline for on demand group is defined as the last non-missing value on or before Day 1 visit. Baseline for fitusiran group is defined as the last non-missing value before 1st dose of fitusiran or the last non-missing value on or before randomization date for patients who were randomized but never exposed to fitusiran.

ECG measurements are taken in triplicate. For the on demand group, the average of the first triplicate readings on or before Day 1 visit or on screening visit will be used as baseline. For fitusiran group, the average of the last triplicate readings before 1st dose is used as baseline.

For questionnaire assessments, the last non-missing value on or before Day 1 visit will be used as baseline. For fitusiran patients, the last non-missing value on or before date of 1st dose of fitusiran or the last non-missing value on or before randomization date for patients who were randomized but never exposed to fitusiran will be used as baseline.

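### The Haem-A-QoL baseline may be completed after open-label allocation, so the covariate in the last confirmatory step is not protected by randomisation

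*Protocol*

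**What the plan says.** **Schedule.** In Protocol Table 1 the Haem-A-QoL/Haemo-QOL row is marked at Day 1 and at EOS, and is blank at Screening. Footnote s adds: "Must be completed at the clinic. Will be collected at EOS visit; not collected at ET visit". Under the schedule, each patient has one baseline value, taken at the Day 1 visit.

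**Randomisation.** Footnote e to Table 1: "Randomization may occur within 3 days prior to Day 1". SAP 5.2: "The Day 1 visit date should coincide with randomization date but could occur within 3 days after the randomization". Protocol 4.5 states that the study is open-label.

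**Order of procedures.** The general note to Table 1 reads "Unless otherwise specified, assessments on dosing days are predose". This sets an order against dosing only. Protocol 7.6.1 ties the choice of form to allocation ("The age of the patient at randomization will determine which age-specific questionnaires will be utilized"), but not the moment of completion.

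**Baseline definition.** SAP 5.5: "For questionnaire assessments, the last non-missing value on or before Day 1 visit will be used as baseline". For fitusiran patients the limit is the date of first dose, and SAP 5.2 allows that date to be later than the Day 1 visit: "If the fitusiran first dose is given after Day 1 visit, a study day will be calculated relative to the day of first dose". Only patients randomised to fitusiran and never dosed have the randomisation date as cut-off.

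**Use.** SAP 6.3.2.4 analyses change from baseline to EOS by ANCOVA with the baseline scores as covariates. SAP 5.7 places Haem-A-QoL (physical health, then total score) as step 5, the last, of the sequence at two-sided 0.05. One planned sensitivity analysis removes baselines completed after the first fitusiran dose.

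**The concern.** ANCOVA adjusts for a baseline imbalance on the footing that the imbalance arose by chance, before treatment was assigned. A self-reported score given after the patient knows his arm does not meet that condition. A patient told that he will continue on-demand treatment, or that he will start prophylaxis, may answer differently from how he would have answered an hour earlier. The model would then adjust for a difference that allocation itself created.

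What is at stake is the adjusted difference, and so the test, for the two Haem-A-QoL scores. The exploratory ANCOVA of the Haemo-QOL total score (SAP 6.3.3.4) is exposed in the same way. The planned exclusion of post-dose baselines does not help, because knowledge of the arm starts at disclosure rather than at injection, and on-demand patients receive no injection.

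**Working it through.** **1. Can the baseline follow allocation?**

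| Element | Rule | Source |
|---|---|---|
| Randomisation | Day 1, or up to 3 days before | Protocol Table 1, footnote e; SAP 5.2 |
| Questionnaire | Day 1 visit, in clinic | Protocol Table 1, footnote s |
| Order against dosing | Before dose | Protocol Table 1, general note |
| Order against randomisation | None stated | – |
| Latest accepted value | Day 1 visit; date of first dose for treated fitusiran patients | SAP 5.5 |

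If randomisation precedes Day 1, a questionnaire completed on schedule always follows it. If both fall on Day 1, either order complies with the plan. The note letting Screening assessments within 7 days of baseline stand in for Day 1 does not help, because the questionnaire is not scheduled at Screening.

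**2. Figures in the documents.** There is no SD, slope, effect size or power for Haem-A-QoL. The only sample-size figure concerns the bleeding rate: 14 + 28 = 42 evaluable, 42/0.8 = 52.5, so 53 against 54 planned. It has no bearing here except that 54 at 2:1 gives 36:18, used in step 4.

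**3. Formula.** Let b be the slope of EOS score on baseline, and D the fitusiran-minus-on-demand difference. For change scores the ANCOVA slope is b − 1, so

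estimate = (D_EOS − D_base) − (b − 1) × D_base = D_EOS − b × D_base.

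If knowledge of the arm changes D_base by δ and leaves EOS unchanged, the bias is −b × δ. Higher scores mean greater impairment. If on-demand patients report worse, or fitusiran patients better, δ is negative and the bias is positive, that is, against fitusiran. The reverse shift favours fitusiran. With δ = 0 there is no bias. This takes one baseline covariate; if both baseline scores enter each model, the bias is minus the sum of two such products.

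**4. Illustrative range (assumptions).** Baseline/EOS correlation 0.3 to 0.7, both scores with SD 1 (so slope equals correlation), δ from −0.2 to −0.5 SD, no true effect, EOS answers unaffected by arm knowledge. Simulation, 4,000 runs per setting, 36:18 patients:

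| b | δ | −b × δ | Simulated bias | Two-sided rejection | Of which favouring fitusiran |
|---|---|---|---|---|---|
| 0.3 | −0.2 | 0.06 | 0.060 | 5.9% | 1.7% |
| 0.3 | −0.5 | 0.15 | 0.150 | 7.8% | 0.5% |
| 0.5 | −0.3 | 0.15 | 0.154 | 9.2% | 0.5% |
| 0.7 | −0.2 | 0.14 | 0.133 | 9.4% | 0.5% |
| 0.7 | −0.5 | 0.35 | 0.347 | 36.2% | <0.1% |

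With an assumed 26:13 adult completers, rejection runs from about 5% to 27%. With no shift it is 4% to 6% at both sizes. For negative δ the excess rejections favour on-demand; changing the sign of δ mirrors the table.

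**The case against.** The strongest objections are these.

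- **The size is assumed.** Correct: neither slope nor shift is in the documents, and nothing shows that patients answer differently on learning their arm. Protocol 4.4 says the site contacts the randomisation system; it does not say when the patient is told.
- **The 3-day gap is an allowance.** SAP 5.2 expects Day 1 and randomisation to coincide. That narrows the gap but does not settle the order within the day.
- **The more intuitive direction is conservative.** If on-demand patients report worse, the bias works against fitusiran. That stands for a superiority claim, but the direction is not fixed, and a conservative bias still distorts the estimate and can cost a true finding.
- **An earlier baseline could increase net reporting bias.** If the same shift s persists to EOS, the present baseline leaves (1 − b) × s, which is 0.3s to 0.7s for b of 0.7 to 0.3, whereas a pre-randomisation baseline leaves all of s. The arithmetic is right, but it needs the same shift to persist unchanged for nine months. A chance offset of that kind does not justify a post-allocation covariate.
- **The scope is narrow.** This stands. The bleeding-rate models do not use this baseline. TSQM-9, HAL/pedHAL, EQ-5D, resource use and HJHS are only summarised, and HJHS is administered by a trained professional rather than self-reported.

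**Conclusion.** The gap is real. The plan permits a post-allocation baseline as the covariate in the last confirmatory step, and its safeguards address dosing rather than knowledge of the arm. The size cannot be derived from the documents: 0.06 to 0.35 SD under the stated assumptions, and possibly zero. The plan should be changed, but the primary analysis is not called into question.

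A reader might infer three stronger things that the documents do not support:

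- That the Haem-A-QoL result is biased, or biased towards fitusiran. No shift is shown, and its direction is open.
- That all patient-reported outcomes carry a faulty adjusted analysis. Only Haem-A-QoL and the exploratory Haemo-QOL total score use ANCOVA.
- That moving the baseline cures open-label reporting. Answers at EOS would still be given by patients who know their arm.

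**What to change.** **Patients still to be randomised.** In Protocol Table 1 and 7.6.1, require the questionnaires to be completed in clinic before the randomisation call. Either randomise on Day 1 after completion, or complete them at a clinic visit shortly before randomisation. The cost is loss of the 3-day allowance, or a slightly older baseline and possibly an extra visit. Relying on Screening alone would be worse, since that window reaches back 60 days.

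**Data already collected.** Keep the main baseline definition in SAP 5.5; restricting it to pre-randomisation values would drop patients from the main ANCOVA. In SAP 6.3.2.4:

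1. Extend the existing sensitivity analysis to both arms, excluding baselines completed after randomisation. Use completion time where recorded, because a rule based on dates misses same-day answers given after allocation. Report by arm how many are of unknown order.
2. Add a supportive comparison of EOS scores adjusted only for the randomisation stratum. It avoids the affected covariate and keeps every patient with an EOS score.

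The first analysis will have fewer patients. The second is less precise: with correlations of 0.3 to 0.7, standard errors rise by a factor of about 1/√(1 − 0.09) = 1.05 to 1/√(1 − 0.49) = 1.40. Sample size and alpha do not change.

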#### 8.2.5. Efficacy Analyses

Primary analyses of the primary and secondary endpoints will be based on the ITT Analysis Set.

To control for the familywise error rate in the testing of primary and selected secondary endpoints, a hierarchical testing approach will be used in the following order:

1. ABR in efficacy period (2-sided alpha = 0.05)
2. ABR in treatment period (2-sided alpha = 0.05)
3. Annualized spontaneous bleeding rate in efficacy period (2-sided alpha = 0.05)
4. Annualized joint bleeding rate in efficacy period (2-sided alpha = 0.05)
5. Change in physical health score and total score of Haem-A-QOL in treatment period (2-sided alpha = 0.05)

If testing of any of the endpoints is not statistically significant, testing of subsequent endpoints will stop and the null hypothesis for subsequent tests will not be rejected. The testing of the secondary endpoint ABR in the onset period will not be included in this hierarchical testing procedure.

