5.7 Multiple Comparisons/Multiplicity

To control for the familywise error rate at 0.05 level in the testing of primary and selected secondary endpoints, a hierarchical testing approach will be used. The endpoints will be tested in the following order:

Global protocol	US protocol	2-Sided alpha
1. ABR in the efficacy period	1. ABR in the treatment period	0.05
2. ABR in the treatment period	2. ABR in the efficacy period	0.05
3. Annualized spontaneous bleeding rate in the efficacy period		0.05
4. Annualized joint bleeding rate in the efficacy period		0.05
5. Change in Haem-A-QOL physical health score and total score in the treatment period		0.05

If testing of any of the endpoints is not statistically significant, formal testing of subsequent endpoints will stop and the null hypothesis for subsequent tests will not be rejected. For endpoint 5, change in Haem-A-QOL physical health score in the treatment period will be tested first followed by change in Haem-A-QOL total score in the treatment period. The testing of the secondary endpoint ABR in the onset period will not be included in this hierarchical testing procedure.

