6.3.2.4 Haem-A-QoL

The Haem-A-QoL will be provided to patients ≥17 years of age, and includes 46 items contributing to 10 QoL domains (physical health, feelings, view of yourself, sports and leisure, work and school, dealing with hemophilia, treatment, future, family planning, partnership and sexuality). Scoring for each item is based on a 5-point Likert scale (never, rarely, sometimes, often, and all the time), and higher scores represent greater impairment. The change from baseline in physical health score and total score of Haem-A-QoL at the end of the study will be analyzed using an analysis of covariance (ANCOVA) model with fixed effects of treatment arm and the randomization strata of number of bleeding episodes in the 6 months prior to study entry (≤10 vs >10), baseline Haem-A-QoL physical health score and total score, as covariates. Least square means of the physical health score and total score in each treatment arm and the difference of the least square means of the physical health score and total score in the two arms (along with the 95% CI and p-value) will be presented. The normality assumption based on ANCOVA model will be examined and a sensitivity analysis based on the non-parametric Wilcoxon-Mann-Whitney test will be performed. Domain scores, standardized scale scores, and transformed scale scores for Haem-A-QoL and their changes from baseline will be summarized. The above ANCOVA analysis is based on observed data. For patient with missing assessment due to early withdrawal, a sensitivity analysis will also be performed by imputing the domain score and total score as the worst score if the reason of withdrawal is treatment-related in the corresponding treatment arm, and as the average score for other reasons of withdrawal that are not treatment related in the corresponding treatment arm. The same analysis as main will be performed as a sensitivity analysis by excluding values of those who completed Haem-A-QoL at baseline after first dose of fitusiran.

To evaluate the impact of Covid-19, the same ANCOVA model will also be repeated on Covid-19 unaffected set. In addition, a sensitivity analysis using same ANCOVA model will be performed excluding the data impacted by Covid-19 major/critical protocol deviation. A supportive analysis will be repeated on the patients whose responses level to EQ-5D dimensions “anxiety/depression” is no change or improved from baseline.

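### Haem-A-QOL is not collected at the early termination visit, so a patient aged 17 or older who withdraws before EOS has no post-baseline score for the step-5 endpoint

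*Protocol*

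**What the plan says.** **Collection.** In Protocol Table 1 the row "Haem-A-QOL / Haemo-QOL" has two marks: Day 1, and the EOS/ET column (Day 253 ±7) with footnote s. There is none at the visits between, including EOT on Day 225. Footnote s adds "Will be collected at EOS visit; not collected at ET visit". The same footnote governs HJHS, resource use, EQ-5D, HAL/pedHAL and TSQM-9.

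**Early leavers.** Footnote b says that, for patients who withdraw early and decline the remaining visits, "every effort should be made to conduct the assessments performed at the EOS/ET visit". Protocol 5.3.2 makes a similar request. Protocol 5.3.1 encourages patients who stop IMP to stay in the study to its end.

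**Testing.** The Haem-A-QOL change is step 5 of the hierarchy, at two-sided 0.05 (Protocol 8.2.5; SAP 5.7). Within that step, "change in Haem-A-QOL physical health score in the treatment period will be tested first followed by change in Haem-A-QOL total score".

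**Analysis.** SAP 6.3.2.4: "The change from baseline in physical health score and total score of Haem-A-QoL at the end of the study will be analyzed using" an ANCOVA, and "The above ANCOVA analysis is based on observed data". The same section turns to withdrawals with "For patient with missing assessment due to early withdrawal" and specifies a sensitivity analysis. It imputes the worst score when the withdrawal was treatment-related and the average score otherwise.

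**The concern.** Protocol 8.2.5 bases the secondary endpoints on the ITT set. With one post-baseline assessment, and that one withheld at ET, the main Haem-A-QOL comparison can include only patients who reach EOS. That makes the sensitivity analysis the main protection against dropout that differs between arms or depends on outcome. It has no post-baseline score from any leaver to work with, although sites are asked to bring those patients in for an ET visit.

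The trial is open-label and the outcome is self-reported, so dropout related to how patients feel is plausible, although the documents give no evidence either way. At stake is how far a step-5 result could be trusted if withdrawals are not few. The four bleeding-rate tests ahead of it are untouched.

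**Working it through.** **1. The plan's own figure.** Inputs from Protocol 8.1: 14 evaluable on-demand patients, 20% drop-out; 2:1 allocation from Protocol 4.4.
- 14 / (1 − 0.20) = 17.5, rounded up to 18; 18 × 3 = 54 randomized. This agrees with the plan.
- Neither document gives a power or sample size for Haem-A-QOL.

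**2. Scheduled post-baseline scores, by type of patient** (Table 1 with footnote s; Protocol 5.3.1; SAP 6.1).
- Completes to EOS: one.
- Stops fitusiran, stays to EOS: one.
- Withdraws, but only after completing the Month 9 visit (counted separately in SAP 6.1): can have one.
- Withdraws from the study before EOS: none.

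The Endpoint row in SAP 5.10, which takes the last post-baseline value up to EOS/ET, has nothing to pick up for the last group, because no earlier assessment is scheduled.

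**3. How many patients.** The instrument is for patients aged 17 or older. The plan expects about 5 patients aged 12 to under 18 but does not say how many are under 17. I assume a range of 0 to 5, which gives 54 to 49 eligible patients.
- 20% drop-out: 0.20 × 54 = 10.8 and 0.20 × 49 = 9.8, so about 10 to 11 without a score.
- 10% drop-out (assumed): 0.10 × 54 = 5.4 and 0.10 × 49 = 4.9, so about 5.

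These are also upper limits on what an ET questionnaire could recover, since some leavers will attend no ET visit.

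**4. What the robustness check must guard against.** The observed-case mean of an arm is displaced by (share missing) × (leaver minus completer gap). The gap is an assumption. With 20% missing in the fitusiran arm only:
- gap 0.5 SD: 0.20 × 0.5 = 0.10 SD
- gap 1.0 SD: 0.20 × 1.0 = 0.20 SD

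A simulation (40,000 two-sample t-tests per setting, no true difference, leavers worse than completers) gave these rejection rates at nominal 5%:

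| Missing in fitusiran arm | Gap 0.5 SD | Gap 1.0 SD |
|---|---|---|
| 7 of 36 | 6.0% | 9.7% |
| 7 of 33 | 6.1% | 10.2% |
| 4 of 36 | 5.4% | 6.5% |
| 3 of 33 | 5.3% | 5.8% |

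The distortion is small unless both dropout and gap are large. Whether the gap is large is what ET scores would help to show and what the present schedule leaves unobserved.

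**The case against.** The strongest case is that this is a deliberate choice with a safeguard. Footnote s treats a whole group of instruments alike, so it is not a slip on one line. The endpoint is change at the end of the study. An ET score could come at any time before that, even in the onset period, so it does not measure that endpoint. The SAP foresees missing assessments and pre-specifies an analysis for them. All of this stands, and it is why an ET score should not replace the EOS value in the main ANCOVA. It does not explain why the score should go uncollected, and I found no rationale in the documents.

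A reader might also infer four stronger things that the documents do not support:
- *Everyone who stops treatment loses the endpoint.* No. Those who stop IMP but stay to EOS complete the questionnaire.
- *Nothing observed can inform the imputation.* No. The baseline score, bleeding stratum, bleeding data up to withdrawal and reason for withdrawal are recorded, and the planned analysis uses the reason. Only a post-baseline quality-of-life score is absent.
- *Footnote s costs precision.* Losing 20% of patients in both arms raises the standard error by 1/√0.8 = 1.12, about 12%. That is the effect of dropout. With EOS kept as the main value, collecting at ET does not recover it.
- *Footnotes b and s contradict each other.* No. The specific footnote limits the general one.

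**Conclusion.** The point holds as a modest, inexpensive improvement. Withdrawal before EOS leaves a patient aged 17 or older with no scheduled post-baseline Haem-A-QOL score. The step-5 ANCOVA is therefore observed-case among those who reach EOS, and the only planned analysis for withdrawals rests on assumed values. It is also a single imputation, and inserting an average understates variance. By contrast, SAP 6.3.1.2 gives the bleeding data multiple imputation under missing-at-random and copy-reference assumptions.

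The size is up to about 10 to 11 patients at the planned 20% drop-out and about 5 at 10%. This assumes 0 to 5 patients under 17 and uses the sample-size allowance, not observed withdrawals. Any bias in the step-5 test depends on a leaver–completer gap that the documents do not give.

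**What to change.** - **Protocol:** delete the ET exclusion in Table 1 footnote s for Haem-A-QOL, so that it agrees with the general request in footnote b and Section 5.3.2.
- **SAP 6.3.2.4:** keep the scheduled EOS value in the main ANCOVA. In the withdrawal analysis, use the ET score as a predictor in the imputation, and add a sensitivity analysis on the last observed score, in place of purely assumed values.
- **SAP 5.10:** the visit windows would place an ET score from Day 239 onward in the Day 253 window. State explicitly how such a score is handled, so that the main analysis is not changed unintentionally.
- **If it is too late to change collection:** replace the single imputation with reference-based multiple imputation and a tipping-point analysis for both scores.

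The cost is one questionnaire at a clinic visit that sites are already asked to attempt. The downside is that ET scores come at varying times, some possibly in the onset period, and some leavers will provide none. They therefore support the robustness check and not the main estimate.
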